4.2.5 Recording of Serious Adverse Events

Serious adverse events will be recorded on the SAE REPORT FORM using a recognized medical term or diagnosis that accurately reflects the event. SAEs will be assessed by the investigator for severity, relationship to the investigational product, and possible etiologies. See Section 4.2.1 for the definition of SAEs, and Section 4.3 and Section 4.4 regarding guidelines for assessment of severity and relationship, respectively.

For the purposes of study analysis, if the event has not resolved at the end of the study reporting period it will be documented as ongoing. For purposes of regulatory safety monitoring the investigator is required to follow the event to resolution and report to the sponsor the outcome of the event using the SAE REPORT FORM.

4.3 Assessment of Severity

Assessment of severity is one of the responsibilities of the investigator in the evaluation of AEs and SAEs. The determination of severity should be made by a health care professional who is qualified to review AE information, provide a medical evaluation of AEs, and classify AEs based upon medical judgment and the severity categories of *Grade 1, Grade 2, Grade 3, Grade 4, and Grade 5*. Severity of toxicity will be graded according to the NCI CTCAE V4.0, as described in detail in Attachment 1.

Grade refers to the severity of the AE. The NCI CTCAE V4.0 displays Grades 1 through 5 with unique clinical descriptions of severity for each AE based on the general guideline:

Grade 1:	Mild AE
Grade 2:	Moderate AE
Grade 3:	Severe AE
Grade 4:	Life-threatening or disabling AE
Grade 5:	Death related to AE

It is important to distinguish between serious and severe AEs. Severity is a measure of intensity whereas seriousness is defined by the criteria in Section 4.2.1. An AE of severe intensity need not necessarily be considered serious. For example, nausea that persists for several hours may be considered severe nausea, but not an SAE. On the other hand, a stroke that results in only a limited degree of disability may be considered a mild stroke, but would be an SAE.

4.4 Assessment of Relationship

An AE is considered “product-related” for the purposes of regulatory reporting if the investigator, the medical monitor, or the product safety physician assesses the AE as possibly, probably, or definitely related to investigational product. This is not a conclusive determination of causal association between the product and the event.

Whenever the investigator’s assessment is unknown or unclear, the AE is treated as product-related for the purposes of reporting to regulatory authorities. An AE may be deemed to be not related to the product for purposes of regulatory reporting only if the investigator, medical monitor, and product safety physician, if applicable, agree that the AE is not product-related.

The investigator is required to provide an assessment of relationship of AEs and SAEs to the investigational product. A number of factors should be considered in making this assessment including: 1) the temporal relationship of the event to the administration of investigational product; 2) whether an alternative etiology has been identified; and 3) biological plausibility. The following guidelines should be used by investigators to assess the relationship of an AE to investigational product administration.

Relationship assessments that indicate an “Unlikely Relationship” to investigational product:

None: The event is related to an etiology other than the investigational product (the alternative etiology must be documented in the study subject’s medical record).

Remote: The event is unlikely to be related to the investigational product and likely to be related to factors other than investigational product.

Relationship assessments that indicate a “Likely Relationship” to investigational product:

Possible: There is an association between the event and the administration of the investigational product and there is a plausible mechanism for the event to be related to investigational product; but there may also be alternative etiology, such as characteristics of the subject’s clinical status or underlying disease.

Probable: There is an association between the event and the administration of investigational product, a plausible mechanism for the event to be related to the investigational product and the event could not be reasonably explained by known characteristics of the subject’s clinical status or an alternative etiology is not apparent.

Definite: There is an association between the event and the administration of investigational product, a plausible mechanism for the event to be related to the investigational product and causes other than the investigational product have been ruled out and/or the event re-appeared on re-exposure to the investigational product.

For AEs that occur prior to the administration of investigational product, an assessment of protocol relatedness must be made. Protocol-related AEs may occur as a result of procedures required during the screening process (eg, blood collection, washout of an existing medication) prior to the initial administration of investigational product. For AEs that occur before administration of investigational product, only those that are assessed by the investigator as protocol-related should be reported to the sponsor. The following guidelines should be used by investigators to assess the relationship of an AE to a protocol-required procedure:

Protocol related: The event occurred due to a procedure/intervention that was described in the protocol for which there is no alternative etiology present in the subject's medical record.

Not protocol related: The event is related to an etiology other than the study procedure (the alternative etiology must be documented in the study subject's medical record).

4.5 Other Events Requiring Immediate Reporting

The following events must be reported *within 24 hours* by fax to MedImmune Product Safety using the fax notification form:

- 1) Any withdrawal of consent during the study
- 2) Pregnancy or intent to become pregnant*
- 3) All severe (Grade 3 or higher, according to the NCI CTCAE, V4.0) AEs that occur during or after administration of the investigational product through Study Day 84 (Dose Cohorts 1-5 and 9) or Study Day 105 (Dose Cohorts 6-8)
- 4) AEs that are considered to be allergic reactions related to investigational product
- 5) AEs that are considered (by the investigator) to be Grade 1 or higher infusion reactions related to the infusion of the investigational product itself. These usually occur within the first 24 hours after infusion and are characterized by a complex of symptoms that may include flu-like illness, fever, chills/rigors, nausea, urticaria, headache, bronchospasm, angioedema, hypotension, hypoxia, pulmonary infiltrates, acute respiratory distress syndrome, myocardial infarction, ventricular fibrillation, and cardiogenic shock.
- 6) Symptoms suggestive of vasculitis
- 7) Any other event that, in the opinion of the investigator, contraindicates further dosing of the study subject
- 8) Any subject discontinuation from the study

* Subjects who become pregnant or intend to become pregnant during the study period must not receive additional doses of investigational product but will be followed for the duration of the study period and beyond as required to collect outcomes for the pregnancy including: pregnancy outcome and any spontaneous abortions, premature terminations, or stillbirths. The health status of the mother and child including date of delivery and the child's gender and weight should be reported to MedImmune Product Safety after delivery.

4.6 Safety Management During the Study

The MedImmune medical monitor has primary responsibility for the ongoing medical review of safety data throughout the study. This includes immediate review of SAEs and timely review of other AEs reported during the study. The MedImmune Product Safety Specialist has responsibility for the day-to-day safety monitoring of the study, including the receipt, review, investigation, and follow-up of SAEs reported by the clinical study sites.

The SMC will independently review cumulative safety surveillance data, as well as the decisions of the medical monitor regarding dose escalation, on a regular basis throughout the study and make recommendations regarding further conduct of the study. The SMC will also review safety data at other time points in response to AEs felt to be medically significant by the medical monitor. The SMC is composed of at least 2 MedImmune physicians who are not directly involved in the day to day operations of the study, and at least 2 physicians who are not employees of MedImmune.

4.7 Interruption or Discontinuation of Study Dosing in Individual Subjects

An individual subject will not receive any further investigational product if any of the following occur in the subject in question:

- 1) Withdrawal of consent
- 2) Pregnancy
- 3) Any life-threatening (Grade 4 according to the NCI CTCAE V4.0; Appendix 3) clinical event related to MEDI-546
- 4) Anaphylactic reaction (immediate life-threatening IgE-mediated allergic reaction with bronchoconstriction, angioedema, and/or hypotension) to MEDI-546
- 5) Disseminated herpes infection, herpes encephalitis, or ophthalmic herpes infection or serious active infection with CMV or EBV
- 6) Symptoms suggestive of vasculitis
- 7) Any event that, in the opinion of the investigator or medical monitor, contraindicates further dosing of an individual subject

Subjects who are permanently discontinued from MEDI-546 will be followed for the full study period (through Study Day 84 for subjects receiving single IV doses and Study Day 105 for subjects receiving multiple IV doses), including the collection of any protocol-specified blood or urine samples, unless consent is withdrawn.

4.8 Interruption or Discontinuation of Study Dosing and Entry

If any of the following occur, no further administration of investigational product will take place and no further subjects will be entered into the study:

- 1) Death of any subject in which the cause of death is assessed as related to MEDI-546
- 2) Any life-threatening clinical event related to MEDI-546
- 3) Anaphylactic reaction (immediate life-threatening IgE-mediated allergic reaction with bronchoconstriction, angioedema, and/or hypotension) to MEDI-546 in any subject
- 4) Disseminated herpes infection, herpes encephalitis, or ophthalmic herpes infection or serious active infection with CMV or EBV in any subject
- 5) The occurrence of a possible safety signal subsequent to expansion of 2 dose cohorts to a maximum of 8 subjects for safety information
- 6) Any event that, in the opinion of the medical monitor, contraindicates further dosing of study subjects

If one of the above-listed events occurs, a prompt cumulative review of safety data and the circumstances of the event in question will be conducted by the medical monitor and the SMC to determine whether dosing and study entry should be resumed, whether the protocol will be modified, or whether the study will be discontinued permanently. Review and approval by the SMC are required for resumption of the study in the event the study is interrupted because of one of the above-listed events.

4.9 Dose Escalation

Dose Cohort 1 (0.1 mg/kg MEDI-546 as a single IV dose to a single subject) will be started first. Decisions regarding dose escalation will be made by the medical monitor based on the review of all cumulative safety information from the stipulated number of subjects in the preceding lower dose cohort through Study Day 7 for single-dose cohorts (Dose Cohorts 1-5) or Study Day 28 for multiple-dose cohorts (Dose Cohorts 6 and 7) and all cumulative safety data available in all other cohorts.

If there is a possible safety signal from the analysis of safety information for a particular dose cohort (Dose Cohorts 2-9 only) that does not warrant discontinuation but does warrant further investigation prior to dose escalation, then the sponsor may add 4 subjects to the dose cohort for a maximum of 8 subjects in the dose cohort. A maximum of 2 dose cohorts may be expanded to a total of 8 subjects each. If a possible safety signal occurs subsequent to expansion of 2 dose cohorts to a maximum of 8 subjects each, then the study will be

terminated. The SMC, which includes physicians external to MedImmune, will independently review cumulative safety surveillance data and the medical monitor's decisions on dose escalation throughout the study and make recommendations regarding the study progression. The SMC can stop study entry and dosing as it deems necessary.

4.10 Monitoring of Dose Administration As with any foreign protein, infusion reactions and IgE-mediated allergic reactions to dose administration are possible. Therefore, appropriate drugs, such as epinephrine and diphenhydramine, and medical equipment to treat acute anaphylactic reactions must be immediately available, and study personnel must be trained to recognize and treat infusion reactions and allergic reactions such as anaphylaxis.

However, subjects should not be premedicated routinely, because the primary objective of this study is to evaluate the safety and tolerability of the investigational product. If infusion reactions or allergic reactions occur during or after investigational product administration, they should be treated appropriately. If a subject experiences an infusion reaction, premedication according to the physician's judgment should be considered prior to subsequent infusions.

5 Statistical Considerations

5.1 General Considerations

The analysis of study data is the responsibility of MedImmune or its designee. A comprehensive statistical analysis plan will be approved prior to the analysis of the study data.

All data will be provided in data listings sorted by dose cohort. Continuous variables will be summarized by descriptive statistics including N, mean, standard deviation, median, and range. Descriptive statistics for summarizing categorical variables include frequency and percentage. Missing data will be treated as missing and no data will be imputed.

5.2 Sample Size and Power Calculations

A minimum of 33 subjects are planned for this study, with dose cohorts of subjects receiving 6 single IV doses and 3 multiple IV doses of MEDI-546 as follows:

- Dose Cohort 1 (N=1): 0.1 mg/kg MEDI-546 as a single IV dose
- Dose Cohort 2 (N=4): 0.3 mg/kg MEDI-546 as a single IV dose
- Dose Cohort 3 (N=4): 1.0 mg/kg MEDI-546 as a single IV dose
- Dose Cohort 4 (N=4): 3.0 mg/kg MEDI-546 as a single IV dose
- Dose Cohort 5 (N=4): 10.0 mg/kg MEDI-546 as a single IV dose
- Dose Cohort 6 (N=4): 0.3 mg/kg MEDI-546 as a weekly IV dose × 4 doses
- Dose Cohort 7 (N=4): 1.0 mg/kg MEDI-546 as a weekly IV dose × 4 doses
- Dose Cohort 8 (N=4): 5.0 mg/kg MEDI-546 as a weekly IV dose × 4 doses
- Dose Cohort 9 (N=4): 20.0 mg/kg MEDI-546 as a single IV dose

If there is a possible safety signal from the analysis of safety information for a particular dose cohort (Dose Cohorts 2-9 only) that does not warrant discontinuation but does warrant further investigation (prior to dose escalation for Dose Cohorts 2-7), then the sponsor may add 4 subjects to the dose cohort for a maximum of 8 subjects in the dose cohort. A maximum of 2 dose cohorts may be expanded to a total of 8 subjects each. If a possible safety signal occurs subsequent to expansion of 2 dose cohorts to a maximum of 8 subjects each, then the study will be terminated. In addition, Dose Cohorts 2-9 may be expanded by up to 2 additional subjects each if eligible subjects are already in screening at the time 4 subjects have been entered into the dose cohort and there is no possible safety signal to warrant expansion of the dose cohort to a maximum of 8 subjects. Therefore, the maximum number of subjects allowed in the study is 53 (29 + 8 [4×2] + 12 [2×6]). No formal calculation was performed to determine sample size because safety is the primary outcome and this will be assessed with descriptive analyses.

[Table 5.2-1](#) and [Table 5.2-2](#) present the probability of observing at least one infrequently occurring event when assuming a range of potential observed event rates and exact binomial 95% confidence intervals to assess the precision of estimates of the event rate for each cohort (n=1 or n=4) and for some cohorts (n=8, 12, 16, 20, 24, 28, respectively) combined.

Table 5.2-1 Expected Number of Events and Probabilities of Observing at Least 1 or 2 Events Given the True Event Rates

N	True Event Rate (%)	Number of Events Expected	Probability of Observing at Least 1 Event (%)	Probability of Observing at Least 2 Events (%)
1	5.0	0	5.0	0.0
1	10.0	0	10.0	0.0
4	2.0	0	7.8	0.2
4	10.0	0	34.4	5.2
8	0.8	0	6.2	0.2
8	6.0	0	39.0	7.9
8	7.0	1	44.0	10.3
12	0.5	0	5.8	0.2
12	4.0	0	38.7	8.1
12	5.0	1	46.0	11.8
16	0.5	0	7.7	0.3
16	3.0	0	38.6	8.2
16	4.0	1	48.0	13.3
20	0.5	0	9.5	0.4
20	2.0	0	33.2	6.0
20	3.0	1	45.6	12.0
24	0.2	0	4.7	0.1
24	2.0	0	38.4	8.3
24	3.0	1	51.9	16.1
28	0.2	0	5.5	0.1
28	2.0	1	43.2	10.7

Table 5.2-2 Estimated Event Rates and 95% Exact Binomial Confidence Intervals Given the Number of Events Observed

N	Number of Events Observed	Estimated Event Rate (%)	95% Confidence Interval
1	0	0.0	(0.0%, 97.5%)
1	1	100.0	(2.5%, 100.0%)
4	1	25.0	(0.6%, 80.6%)
4	2	50.0	(6.8%, 93.2%)
8	1	12.5	(0.3%, 52.7%)
8	2	25.0	(3.2%, 65.1%)
12	1	8.3	(0.2%, 38.5%)
12	2	16.7	(2.1%, 48.4%)
16	1	6.3	(0.2%, 30.2%)
16	2	12.5	(1.6%, 38.3%)
20	1	5.0	(0.1%, 24.9%)
20	2	10.0	(1.2%, 31.7%)
24	1	4.2	(0.1%, 21.1%)
24	2	8.3	(1.0%, 27.0%)
28	1	3.6	(0.1%, 18.3%)
28	2	7.1	(0.9%, 23.5%)

5.3 Analysis Populations

All subjects who receive any investigational product will be included in all summaries. Missing data will be treated as missing. No data will be imputed.

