Infusion reactions have been reported with the administration of intravenous gammaglobulin and nearly all approved monoclonal antibodies. For purposes of this protocol, infusion reactions are defined as anaphylactoid-like AEs related to the infusion of the investigational product itself that usually occur within the first 24 hours after infusion, especially within minutes to a few hours, and will be distinguished from true anaphylactic reactions by absence of measurable antibodies against the investigational product. Infusion reactions are characterized by a complex of signs and symptoms that include flu-like illness, fever, chills/rigors, nausea, urticaria, headache, bronchospasm, angioedema, hypotension, hypoxia, pulmonary infiltrates, acute respiratory distress syndrome, myocardial infarction, ventricular fibrillation, and cardiogenic shock. For purposes of this protocol, a classification of infusion reactions is given in [Table 3.4.4-1](#), with suggested treatment options. Final treatment is at the discretion of the investigator and should reflect local standard of care.

Table 3.4.4-1 Classification and Suggested Treatments for Infusion Reactions

Severity of Symptoms	Treatment	Study Drug

Mild (Grade 1)
 
Localized cutaneous reactions such as mild pruritus, flushing, rash, dizziness, headache, ≤ 20 point change in systolic BP
	
 • Stop study drug infusion immediately • Evaluate patient, including close monitoring of vital signs • At the discretion of the investigator, treat patient, for example with 
 – Normal saline (~500-1000 mL/hour IV) – Diphenhydramine 50 mg IV – Acetaminophen 500-650 mg 	
 • Option 1: Do not resume infusion; OR, at the discretion of the investigator, resume current infusion under observation and complete study drug infusion at no more than half the planned infusion rate • Option 2: Discontinue further administration of study drug ;OR, at the discretion of the investigator, continue study drug administration and consider slowing infusion rate and pretreating patient 1.5-0.5 hours prior to study drug administration, for example with 
 – Diphenhydramine 50 mg IV – Acetaminophen 500-650 mg

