
Severe (Grade 3) or
 
Above plus fever with rigors, hypo- or hypertension with ≥ 40 point change in systolic BP, wheezing, angioedema, or stridor
 
Life threatening (Grade 4)
 
Defined as a reaction that is life threatening and requires pressor and/or ventilator support or shock associated with acidemia and impairing vital organ function due to tissue hypoperfusion
	
 • Stop study drug infusion immediately • Evaluate patient, including close monitoring of vital signs • Maintain airway, oxygen if available • Treat patient immediately, for example with 
 – Normal saline (~500-1000 mL/hour IV) – Epinephrine for bronchospasm, hypotension unresponsive to IV fluids, or angioedema. Dose and route as per local standard of care, example, epinephrine 1:1000, 0.5-1.0 mL administered SC for mild cases and IM for more severe cases – IV corticosteroids, such as hydrocortisone 100 mg or methylprednisolone 20-40 mg – Diphenhydramine 50 mg IV – Acetaminophen 500-650 mg • Call emergency medical transport for transport to hospital if 
 – Grade 3 wheezing, hypotension or angioedema is unresponsive to single dose of epinephrine – Grade 4 – At the discretion of the investigator 	
 • Do not resume infusion • Discontinue further study drug administration

If an infusion reaction occurs during or after investigational product administration, the subject will remain at the study site for a minimum of 2 hours for observation after resolution of symptoms and undergo the following procedures unless transferred to an emergency or hospital facility is deemed warranted for a more severe reaction:

- Clinical evaluation, treatment, and stabilization of the subject according to standard medical practice, with suggested approaches outlined above;
- Close monitoring of vital signs, for example every 5 to 10 minutes for Grade 1 or Grade 2 infusion reactions and every 2 to 5 minutes for Grade 3 or Grade 4 infusion reactions until stable;
- Collect serum for assessment of safety biomarkers (including serum levels of mast cell tryptase, cytokines/chemokines, and IgE antibodies) for Grade 1 or higher infusion reactions as soon as possible after the event, at 60 minutes after the event, and at discharge.

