5.5.1 Pharmacokinetics

Serum MEDI-546 concentration data will be tabulated by dose cohort together with descriptive statistics. Individual and mean serum concentration-time profiles of MEDI-546 by dose cohort will be generated and included in the report. Noncompartmental PK data analysis will be performed using the software package WinNonlin[®]. For PK data analysis, time zero is defined as the end of infusion. The PK parameters to be obtained and reported include, but are not limited to:

- C_{\max} - the maximum observed serum concentration of MEDI-546 following IV infusion
- T_{\max} - the time of the observed C_{\max}
- $AUC_{0-\infty}$ - the area under the serum concentration - time curve from time zero to infinity;
- AUC_{0-t} - the area under the serum concentration – time profile from time zero to the last measurable time point
- AUC_{0-7d} - the area under the serum concentration – time profile from time zero to 7 days post dose (for Dose Cohorts 6-8)
- $t_{1/2}$ - the terminal elimination half-life;
- CL - systemic clearance;

Descriptive statistics of noncompartmental PK parameters by dose cohort will be provided in the report. If the data allow, compartmental modeling may be performed to further

characterize the PK and the PK-PD relationship of MEDI-546 in scleroderma subjects. However, due to the exploratory nature of the study, the actual modeling work may not be reported.

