5.5.3 Pharmacodynamics

The level of receptor occupancy will be determined by flow cytometry as a measure of the binding of labeled MEDI-546 in the presence of dosed levels of MEDI-546. Total type I IFNAR levels will be assessed using a separate anti-IFNAR1 antibody that binds to a distinct epitope from MEDI-546.

The level of expression of type I IFN-inducible genes will be determined in whole blood and skin mRNA, using Affymetrix technology. Results will be listed by dose group with mean and individual results at different time points. Changes from baseline will be described and PD assessed. Relationships between receptor occupancy and inhibition of type I IFN gene signature will be explored.

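### Section 5.3 puts every treated subject into all summaries, so a subject who is partly infused or stops weekly dosing early would enter the PK and PD cohort means at the nominal dose

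*Protocol*

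**What the plan says.** Section 5.3 is the protocol's only analysis-population rule: "All subjects who receive any investigational product will be included in all summaries". It continues: "Missing data will be treated as missing. No data will be imputed".

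PK and PD are reported by planned dose. Section 5.5.1: "Descriptive statistics of noncompartmental PK parameters by dose cohort will be provided in the report". Section 5.5.3: "Results will be listed by dose group with mean and individual results at different time points".

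Incomplete dosing is foreseen. For Grade 1 and 2 infusion reactions, the first option in Table 3.4.4-1 (Section 3.4.4) reads "Do not resume infusion; OR, at the discretion of the investigator, resume current infusion under observation", and later doses may be stopped. For Grade 3 and 4 reactions the table says "Do not resume infusion". Section 4.7 lists further events that end a subject's dosing.

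Sampling goes on afterwards. Section 4.7: "Subjects who are permanently discontinued from MEDI-546 will be followed for the full study period", "including the collection of any protocol-specified blood or urine samples, unless consent is withdrawn". Section 3.5 likewise keeps anyone who received drug in follow-up, however many doses were given.

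Sections 2.4 and 3.2 define evaluability for safety (Day 7, or stopping for safety reasons) and for exploratory endpoints (Day 28). Neither covers PK or PD, and Section 5.3 does not refer to them. Replacement is allowed only for reasons other than safety.

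**The concern.** Including everyone treated is right for safety. For PK and PD, a cohort mean is read as describing the dose on its label. A subject who received part of one infusion, or one of four weekly doses, supplies real samples that reflect a different exposure. These values exist, so the missing-data rule does not remove them, and Section 5.3 as written puts them in the mean.

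Cohorts 2 to 9 are planned at four subjects, so one such subject carries a quarter of the weight. A subject who stops for safety counts as evaluable and is not replaced. If reactions are more frequent at higher doses, the understatement would fall mainly there and flatten the apparent relation between dose and exposure.

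The protocol fixes this rule itself. An SAP that left such subjects out of the PK or PD summaries would contradict Section 5.3.

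**Working it through.** The protocol attaches no figure to this point, so there is none to reproduce.

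**Inputs from the protocol:** four subjects per cohort (Section 5.2); weekly doses on Days 0, 7, 14 and 21 (Section 3.4.2); serum sampling on Day 28 (Table 3.5-2).

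**Assumptions:** exposure proportional to dose, first-order elimination, and a half-life of 3 to 14 days. The protocol gives no human half-life; Section 1.3 says only that in monkeys it was under a week in most dose groups.

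**1. One partial single infusion.** If one of n subjects receives a fraction f, the cohort mean changes by (n − 1 + f)/n − 1.

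| f | n = 4 | n = 8 |
|---|---|---|
| 0.25 | 3.25/4 − 1 = −18.75% | 7.25/8 − 1 = −9.4% |
| 0.50 | 3.50/4 − 1 = −12.5% | 7.50/8 − 1 = −6.25% |
| 0.75 | 3.75/4 − 1 = −6.25% | 7.75/8 − 1 = −3.1% |

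**2. One subject stopping after dose 1 of 4, Day 28 concentration.** Let r = 2^(−7/t½). A fully dosed subject has a concentration proportional to r + r² + r³ + r⁴; a subject given only the Day 0 dose has r⁴. The ratio is r⁴/(r + r² + r³ + r⁴), and the mean of four changes by −(1 − ratio)/4.

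| t½ (days) | r⁴ | Full sum | Ratio | Change in mean |
|---|---|---|---|---|
| 3 | 0.00155 | 0.247 | 0.006 | −24.8% |
| 7 | 0.0625 | 0.9375 | 0.067 | −23.3% |
| 14 | 0.25 | 1.811 | 0.138 | −21.5% |

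Over the same half-lives, stopping after two doses lowers the mean by 24.1% to 16.7%, and stopping after three doses by 20.1% to 9.8%.

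**3. Clearance.** Section 5.5.1 does not say which dose enters CL. With CL = dose/AUC and AUC proportional to the dose received, using the planned dose multiplies that subject's CL by 1/f. At f = 0.5 the mean of four becomes (3 + 2)/4 = 1.25 times the true value. Using the infused dose removes this error.

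**4. How often.** The protocol gives no rate of incomplete dosing. At an assumed 5% or 10% per subject, independent between subjects, 1 − (1 − p)^n gives an 18.5% or 34.4% chance of at least one in a cohort of four, and 81.6% or 96.9% among the planned minimum of 33.

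**The case against.** The strongest case on the other side is that little depends on these means. No treatment groups are formally compared (Section 5.4), escalation rests on safety data (Section 4.9), and the PK/PD-based choice of doses for Cohorts 6 to 8 has already been made by modelling (Section 1.4). Section 5.1 lists all data by cohort and adds medians and ranges, and Sections 5.5.1 and 5.5.3 also report individual results, so among four subjects a deviating one would be seen. Infusions stopped for Grade 1 or 2 reactions may be resumed. Several Section 4.7 events also halt dosing in the whole study under Section 4.8. A cohort with a possible safety signal may grow to eight, which halves the shifts for a partial infusion. All of this stands. It limits the weight of the point, but the reported means would still be mislabelled.

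A second objection also stands: dropping subjects because of a reaction selects on a post-dose event. That argues for showing both summaries rather than excluding anyone outright.

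That the SAP may define a PK set does not answer the point, because Section 5.3 already says otherwise.

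Three stronger readings are tempting but unsupported:

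- A reader might infer that the Day 28 biopsy result falls by the same 21% to 25%. That figure is a serum concentration. The biopsy measures gene expression, and nothing in the protocol makes inhibition proportional to concentration; Section 5.7 treats it as a threshold of 70%.
- A reader might infer that the relation between receptor occupancy and gene signature is corrupted. Section 5.5.3 says only that it will be explored and does not tie it to cohort means. Compared within subjects, an incompletely dosed subject is a valid point.
- A reader might infer that the means will be wrong. The problem arises only if a subject is in fact partly infused or stops early.

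**Conclusion.** The point holds as a conditional one. Followed as written, Section 5.3 places any incompletely dosed subject in PK and PD means labelled with the planned dose. For one such subject in a cohort of four, mean exposure after a partial single infusion (25% to 75% given) is about 19% to 6% too low. The mean Day 28 serum concentration after a stop at dose 1 of 4 is about 21% to 25% too low.

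These figures rest on linear kinetics and, for Day 28, on half-lives of 3 to 14 days. Section 1.3 reports a more than dose-proportional rise in AUC in monkeys; if that held in humans, the loss of AUC after a partial infusion would be larger. In Cohorts 6 to 8, results obtained before the stop, such as AUC over the first 7 days after a complete first dose, are unaffected. The size of any effect on gene signature is unknown.

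PK and PD are secondary and descriptive, and individual results are shown. The change is still worth making because it costs little and Section 5.3 as worded rules out the more accurate summary.

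**What to change.** - In Section 5.3, limit the all-treated rule to safety and immunogenicity. The rule now also covers the exploratory summaries, so state their population separately.
- For PK and PD, give by-cohort summaries at each time point for subjects who received all planned infusions up to then. Show the all-treated summary beside them, with the number of subjects in each.
- Flag incompletely dosed subjects in listings and plots.
- In Section 5.5.1, state that CL is computed from the dose actually infused.
- Keep every treated subject in concentration-based or subject-level PK-PD plots, where actual exposure or the subject's own measurements are compared.
- If a near-complete infusion is to count as complete, the sponsor should pre-specify the threshold. The protocol offers no basis for a particular value.

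The cost is a few sentences in Sections 5.3 and 5.5, plus recording the infused volume whenever an infusion is interrupted. Some cohort summaries may rest on three subjects, which should be stated where it occurs. No data are discarded and no clinical rule changes.
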